## **10.** DEMOGRAPHIC AND OTHER BASELINE CHARACTERISTICS

Demographic data and other baseline characteristics will be summarized descriptively for the ITT Analysis Set. No statistical testing will be carried out for demographic or other baseline characteristics. Subject characteristics may include, but are not limited to:

- Age (years) calculated relative to date of informed consent
- Gender
- Race
- Ethnicity
- Region
- Weight (kg)
- Height (cm)
- Body Mass Index (BMI) (kg/m^2)
- Schizophrenia Diagnosis
  - o Time since first diagnosis of Schizophrenia (years)
  - o Time since start of current exacerbated episode (weeks)
- Schizophrenia Baseline Efficacy
  - Baseline PANSS total score (< 90, >= 90), Baseline MSQ score
- Age (years) of first diagnosis of schizophrenia
- Antipsychotics treatment before current episode (yes/no)

## **10.1.** DERIVATIONS

- BMI  $(kg/m^2)$  = weight  $(kg)/height (m)^2$
- Time since first diagnosis of Schizophrenia (years) =

(Date of first dose of double-blind study medication - date of first diagnosis)/365.25

• Time since start of current exacerbated episode (weeks) =

(Date of first dose of double-blind study medication - start date of current exacerbated episode)/7

Document:	\\quintiles.net\Enterprise\Apps\sa	sdata\SASb\SAS\Noven\HP-	
	3070\XWA17541\Biostatistics\Documentation\SAP\Final 6\Noven HP-3070-GL-04 SAP text Final		
	6_18Jan2018.docx		
Author:	[name]	Version Number:	Final 6
		Version Date:	18Jan2018
Template No:	CS TP BS016 – Revision 3	Reference: (	CS WI BS005

Effective Date: 01May2012

Copyright © 2012 Quintiles Transnational Corp. All rights reserved.

Noven Pharmaceuticals, Inc. STATISTICAL ANALYSIS PLAN: PROTOCOL HP-3070-GL-04 Page 23 of 50

# **11. MEDICAL HISTORY**

Medical History information will be presented in listings only.

Medical History will be coded using Medical Dictionary for Regulatory Activities (MedDRA).

# **12.** STUDY MEDICATION EXPOSURE

To ensure treatment compliance, patches will be applied and removed by designated qualified staff. The exact times of patch application and removal will be recorded on the eCRF. The date of first and last doses of double-blind study medication administration will be taken from the eCRF.

The date and time of first dose of double-blind study medication will correspond to the date and time when the first double-blind patch is applied for each subject. The date and time of the last dose of double-blind study medication will correspond to the date and time when the last patch of double-blind study medication is removed.

Exposure to study medication will be summarized in terms of duration of exposure (days) to the double-blind study medications for the Safety analysis set by treatment group.

Duration of exposure to the double-blind study medication will be summarized by treatment group as a continuous variable. Additionally, duration of exposure to the double-blind study medication will be summarized in terms of the number and percentage of subjects with exposure for less than 1 week, and at least 1, 2, 3, 4, 5, and 6 weeks. The total number of patches applied will also be summarized for the double-blind period and by week.

# 12.1. DERIVATIONS

Duration of exposure (days) to the double-blind study medication will be calculated as (date of last dose of double-blind study medication) – (date of first dose of double-blind study medication) + 1.

# **13.** STUDY MEDICATION COMPLIANCE

Compliance with study medication during the double-blind period will be summarized for the ITT analysis set.

During the double-blind Treatment Period (Day 1 through Day 42) site personnel will apply 2 patches once daily to subjects as randomized. Patches will be applied by site personnel at approximately the same time every day and each patch will be worn for 24 hours.

If both patches are detached completely then 2 new patches from the subject's kit should be applied immediately, provided that there is at least 6 hours of time remaining before the next dose. If only one patch detaches completely, then the other patch should also be removed and 2 new patches from the subject's kit should be applied immediately, provided that there is at least 6 hours of time remaining before the next dose.

Document:	\\quintiles.net\Enterprise\Apps\sasdata\SASb\SAS\Noven\HP- 3070\X\\\A17541\Biostatistics\Documentation\SAP\Einal 6\Noven HP-3070-GL-04 SAP text Einal			
	6_18Jan2018.docx			
Author:	[name]	Version Number:	Final 6	
		Version Date:	18Jan2018	
Template No: CS_TP_BS016 – Revision 3 Effective Date: 01May2012		Reference:	CS_WI_BS005	

Copyright © 2012 Quintiles Transnational Corp. All rights reserved.

Noven Pharmaceuticals, Inc. STATISTICAL ANALYSIS PLAN: PROTOCOL HP-3070-GL-04 Page 24 of 50

Number and percentage of subjects who are compliant (defined as using  $\geq$  80% and  $\leq$  120% of study medication) and noncompliant (defined as using less than 80% or more than 120% of study medication) during any evaluation period will be presented.

Compliance will be summarized for periods between every double-blind treatment period visit (Weeks 1 through 6) and double-blind period overall.

# 13.1. DERIVATIONS

Compliance with study medication (based on the drug accountability and patch application and removal data) will be calculated as the number of patches applied divided by the prescribed number of patches over a given period, expressed as a percentage.

Patches are prescribed once daily, 2 patches per administration, on the days while the subject remains on study treatment during the double-blind treatment period.

The number of patches that needed to be replaced due to detachment more than 6 hours before the next dose (as described in Section 13) will be counted in the number of patches prescribed. Similarly, the number of patches that were applied as a result of such detachment will be counted in the total number of patches applied.

# 14. MEDICATIONS

Medications taken from 6 months prior to the Screening visit through the End of Study (including follow-up period) must be recorded and will be summarized for the Safety analysis set as either prior, concomitant, or post-treatment medications. All medications will be coded using World Health Organization Drug Dictionary (WHO-DD) version 19.

Prior medications are medications which started and stopped prior to the first dose of double-blind study medication. Prior medications that stopped within the six months prior to screening medication will be summarized. All medications reported on the eCRF will be included in the listing.

Concomitant medications are medications which are administered to the subject during the period of time starting at the date of first dose of double-blind study medication up to 1 day after the date of last dose of study medication. They include medications which:

• started on, or after the first dose of double-blind study medication (no later 1 day following the date of last dose of study medication), and

• ended on or after the date of first dose of double-blind study medication or were ongoing at the end of the study.

Post-treatment medications are medications which started more than 1 day after the date of last dose of doubleblind study medication.

In the case where it is not possible to define a medication as prior, concomitant, or post-treatment, the medication will be classified as concomitant.

_				
Document:	\\quintiles.net\Enterprise\Apps\sasdata\SASb\SAS\Noven\HP-			
	3070\XWA17541\Biostatistics\Docur	mentation\SAP\Final 6\Noven HP-3070-GL-04 S	AP text Final	
	6_18Jan2018.docx			
Author:	[name]	Version Number:	Final 6	
		Version Date:	18Jan2018	
Template No: CS_TP_BS016 – Revision 3		Reference: 0	CS_WI_BS005	
Effective Date:	01May2012			

Copyright © 2012 Quintiles Transnational Corp. All rights reserved.

Noven Pharmaceuticals, Inc. STATISTICAL ANALYSIS PLAN: PROTOCOL HP-3070-GL-04 Page 25 of 50

Number of subjects with concomitant medications will be summarized by WHO-DD Preferred Term, overall and by treatment group for the Safety Analysis Set. Multiple occurrences of medications coded to the same PT in a subject will be counted only once within the PT.

The following algorithm will apply to partial dates. Imputed dates will NOT be presented in the listings but may be used to determine the category of medications (prior, concomitant, or post-treatment).

If a medication, as reported on the eCRF, has a partially or completely missing start or end date, use the following algorithm to impute missing components of the date(s). Imputed dates will be used in order to determine prior/concomitant/post-treatment status of a therapy.

Let CMSTDTC represent the medication start date and CMENDTC represent the medication stop date.

If a therapy has some missing components in both the start and end dates, first impute the end date as follows (only if the therapy is not ongoing):

- 1. If CMENDTC contains only year and month impute the missing day to the last day of the corresponding month (e.g., 31 for January, or 30 for April).
- 2. If CMENDTC contains only year impute the missing day and month to the 31st of December of the corresponding year.
- 3. If CMENDTC is completely missing impute to the date of the last contact with the subject.

Note: The end date should remain null for medications that are ongoing.

After having imputed the end date (if needed), impute the therapy start date if it is partial or missing as follows:

- 1. If CMSTDTC contains only year and month impute the missing day to the 1st day of the corresponding month.
- 2. If CMSTDTC contains only year impute the missing day and month to the 1st of January of the corresponding year.

If CMSTDTC is completely missing impute to the date of informed consent or to the medication end date (previously imputed if needed), whichever is earlier.

## **15. EFFICACY OUTCOMES**

#### **15.1. PRIMARY EFFICACY**

#### **15.1.1. PRIMARY EFFICACY VARIABLE & DERIVATION**

The primary efficacy endpoint is the change in PANSS total score between Baseline and Week 6.

The PANSS consists of 3 subscales containing a total of 30 items. For each item, severity is rated on an anchored 7-point scale, with a score of 1 indicating the absence of symptoms and a score of 7 indicating extremely severe

Document:	\\quintiles.net\Enterprise\Apps\sasdata\SASb\SAS\Noven\HP-		
	3070\XWA17541\Biostatistics\Documentation\SAP\Final 6\Noven HP-3070-GL-04 SAP text Final		
	6_18Jan2018.docx		
Author:	[name]	Version Number:	Final 6
		Version Date:	18Jan2018
Template No:	CS_TP_BS016 – Revision 3	Reference: 0	CS_WI_BS005

Effective Date: 01May2012

Copyright © 2012 Quintiles Transnational Corp. All rights reserved.

Noven Pharmaceuticals, Inc. STATISTICAL ANALYSIS PLAN: PROTOCOL HP-3070-GL-04 Page 26 of 50

#### symptoms.

The PANSS total score is the sum of all 30 items. The score ranges from 30 through 210, with higher values representing greater severity of illness.

If one or more items are missing at a given assessment, the total score will be set to missing.

#### 15.1.2. MISSING DATA METHODS FOR PRIMARY EFFICACY VARIABLE

Missing PANSS total scores will not be imputed for primary analysis. The primary analysis method, MMRM, will utilize all data available during the double-blind treatment period (complete and partial) from subjects included in the analysis set.

Analysis of sensitivity to missing data for the primary endpoint will be performed as described in Section 15.1.4.

Missing data patterns will be described graphically by plotting mean changes from baseline in PANSS total score, positive, negative and general psychopathology subscales across visits by treatment group and subgroups of subjects that either completed the double-blind treatment period or discontinued early. Subjects who discontinued early will be grouped by week at which they discontinued (1 through 6).

#### 15.1.3. PRIMARY ANALYSIS OF PRIMARY EFFICACY VARIABLE

The primary efficacy analysis will be performed for the Full Analysis Set.

The estimand in the primary analysis for efficacy for each dose is the difference between treatments groups (HP-3070 dose group vs. placebo) in the change from Baseline to Week 6 in PANSS total score in all subjects as randomized, under the assumption that all randomized patients remain on their randomized treatment throughout the trial. PANSS scores obtained 24 hours after removal of the double-blind study medication on Day 42 or PANSS scores obtained more than 24 hours after discontinuation of double-blind study medication and the subject switched to an approved antipsychotic treatment will be excluded as outliers. Outliers will be defined *a priori* as (i) PANSS total scores obtained more than 24 hours after removal of double-blind study medication on Day 42; or (ii) PANSS total scores obtained more than 24 hours after discontinuation of double-blind study medication and the subject switched to an approved antipsychotic treatment. Non-compliance/non-adherence to study treatment may lead to poor outcomes and introduce variability. The terminal half-life of asenapine from Saphris/Sycrest is 24 hours and the mean half-life of asenapine from HP-3070 patch ranged from 29.7 hours to 31.3 hours for all the application sites.

Considerable efforts will be made during the study conduct to prevent outliers. For example: site personnel will be instructed to not issue a day pass to patients on Day 41 (last day of double-blind patch application) and patients will be allowed to leave the clinic only after all Day 42 (Week 6) assessments are complete. Subjects without PANSS total score at Week 6 will be modeled as similar to those with data conditional on observed response history and covariates. All discontinued subjects will be assessed with PANSS total score at the time of treatment discontinuation.

The primary efficacy variable, change from Baseline to Week 6 in the PANSS total score for each of the 3 treatment arms, will be analyzed using an MMRM analysis. The MMRM model will include change from Baseline

Document:	\\quintiles.net\Enterprise\Apps\sasdata\SASb\SAS\Noven\HP- 3070\XWA17541\Biostatistics\Documentation\SAP\Final 6\Noven HP-3070-GL-04 SAP text Final		
Author:	6_18Jan2018.docx [name]	Version Number:	Final 6
		Version Date:	18Jan2018
Template No: CS_TP_BS016 – Revision 3		Reference:	CS_WI_BS005

Copyright © 2012 Quintiles Transnational Corp. All rights reserved.

Effective Date: 01May2012

Noven Pharmaceuticals, Inc. STATISTICAL ANALYSIS PLAN: PROTOCOL HP-3070-GL-04 Page 27 of 50

in PANSS total score as the repeated dependent variable, with country, treatment (HP-3070 9 mg, HP-3070 18 mg, and placebo), visit (Weeks 1, 2, 3, 4, 5, and 6), treatment by visit interaction, and the Baseline PANSS total score as covariates. An unstructured covariance matrix will be assumed. In the event the convergence cannot be attained with the unstructured correlation matrix, the following alternative structures will be attempted in the specified order (from least restrictive to most restrictive): heterogeneous Toeplitz structure (TOEPH), heterogeneous autoregressive(1) (ARH(1)), heterogeneous compound symmetry (CSH), No Diagonal Factor Analytic (FA0(q), with q equal to the number of time points), Toeplitz structure (TOEP), autoregressive(1) (AR(1)), and compound symmetry (CS). The first structure in this list with which the model converges will be used. If either ARH(1) or AR(1) structure is used, a random subject intercept will also be included in the model. The Restricted Maximum Likelihood (REML) method will be used for the estimation of the covariance parameters. The Kenward-Rogers method will be used to estimate the denominator degrees of freedom. The treatment-by-time interaction term allows for comparisons of the treatment groups at each time point. Treatment comparisons of each HP-3070 dose to placebo at Week 6 will be used for the primary analysis.

SAS procedure MIXED will be used to perform this analysis as follows:

proc mixed data=<analysis dataset>;

class TRT COUNTRY VISIT SUBJID; model CHG = TRT COUNTRY VISIT TRT\*VISIT BASE / ddfm=kr; repeated VISIT / type=un subject=SUBJID; Ismeans TRT\*VISIT / cl pdiff=all;

run;

The following statistics will be reported based on the MMRM analysis: least squares mean (LSM) estimates for change from baseline in PANSS score at Week 6, standard errors and 95% confidence intervals (CIs) for LSMs by treatment group. LSM differences between treatment groups (i.e., HP-3070 9 mg vs. placebo and HP-3070 18 mg vs. placebo), the corresponding standard errors, 95% CIs, and p-values will be presented for Week 6. P-values corresponding to Week 6 comparisons will be used for inferential purposes of the primary analysis and the comparisons between each of the two HP-3070 doses versus placebo will be adjusted for multiplicity as described in Section 7.4.

Observed values and change from Baseline to Week 6 will also be summarized descriptively.

An MMRM model with heterogeneous variances will be fitted (using a GROUP=<treatment> option in the REPEATED statement of SAS PROC MIXED) and the Akaike's Information Criterion (AIC) from this model will be compared to the AIC value from the primary analysis model. If the AIC value for the model with heterogeneous variances is smaller, the results from this model will be presented.

Residuals and influence diagnostics will be performed for the primary MMRM, and if there is an indication that the normality assumption is violated and/or extremely influential observations are identified.

Model diagnostics will be performed through examination of graphical displays of studentized residuals versus predicted mean, a quantile-quantile plot of studentized residuals, fixed effects influence diagnostics and covariance parameter influence diagnostics. These diagnostic plots will be produced using the ODS GRAPHICS functionality of SAS PROC MIXED (using options RESIDUAL and INFLUENCE(ITER=5 EFFECT=<subject>).

Document:	\\quintiles.net\Enterprise\Apps\sas	data\SASb\SAS\Noven\HP-	
	3070\XWA17541\Biostatistics\Documentation\SAP\Final 6\Noven HP-3070-GL-04 SAP text Final		
	6_18Jan2018.docx		
Author:	[name]	Version Number:	Final 6
		Version Date:	18Jan2018
Template No:	CS TP BS016 – Revision 3	Reference:	CS WI BS005

Effective Date: 01May2012

Copyright © 2012 Quintiles Transnational Corp. All rights reserved.

Noven Pharmaceuticals, Inc. STATISTICAL ANALYSIS PLAN: PROTOCOL HP-3070-GL-04 Page 28 of 50

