## 3. STUDY DESIGN

## **3.1. GENERAL DESCRIPTION**

This is a Phase 3, randomized, double-blind, placebo-controlled, in-patient, safety, and efficacy study to evaluate HP-3070 for the treatment of schizophrenia.

This study will consist of a Screening/placebo Run-in Period of 3 to 14 days, a 6-week double-blind Treatment Period and a 30 day Follow-up Period.

Subjects will be hospitalized at the Screening Visit and will remain hospitalized during the study. The subject may leave the hospital study for necessary personal business. Any subject who leaves the site must have an alcohol breathalyzer and urine drug tests when they return to the site.

After obtaining informed consent, each subject will be assigned a unique subject number. Eligible subjects will be hospitalized for the duration of the study. While undergoing screening procedures and waiting for results of laboratory tests, ECGs, and other assessments, the subject will start treatment with the single-blind placebo patch. The subject must have the single-blind placebo patch applied for a minimum of 3 days prior to being randomized into the double-blind Treatment Period. In addition, current antipsychotic and other prohibited medications will be washed out during the run-in period and must be completed prior to randomization into the double-blind treatment period. Details in regard to wash-out periods for specific drugs are summarized in Protocol Section 5.10.1. Subjects who have a decrease in PANSS total score ≥20% from Screening to Baseline or a PANSS total score <80 at Screening or Baseline will be discontinued from the study and will not enter the double-blind Treatment Period.

Document:	\\quintiles.net\Enterprise\Apps\sasdata\SASb\SAS\Noven\HP-			
Documenti	3070\XWA17541\Biostatistics\Docu	imentation\SAP\Final 6\Noven HP-3070-GL-04 S/	AP text Final	
	6_18Jan2018.docx			
Author:	[name]	Version Number:	Final 6	
		Version Date:	18Jan2018	
Template No:	CS TP BS016 – Revision 3	Reference: C	CS WI BS005	

Effective Date: 01May2012

Copyright © 2012 Quintiles Transnational Corp. All rights reserved.

Noven Pharmaceuticals, Inc. STATISTICAL ANALYSIS PLAN: PROTOCOL HP-3070-GL-04 Page 12 of 50

Subjects eligible for randomization into the double-blind Treatment Period will be randomly assigned to HP-3070 9.0 mg, HP-3070 18.0 mg, or placebo in a 1:1:1 ratio stratified by country. Subjects will receive treatment with study medication daily for 6 weeks.

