The study will evaluate 9.0mg (HP-3070 9.0 mg) and 18.0 mg (HP-3070 18.0 mg) of HP-3070 transdermal patches versus placebo transdermal patches. Patches will be applied by site personnel at approximately the same time daily and each patch will be worn for 24 hours. Every day, 24 hours (±15 minutes) after patch application, site personnel will remove previous day's patches and apply new patches.

All subjects will have a follow-up contact (site visit or telephone call, at the discretion of the Investigator) 30 days after the last patch is removed. This contact will be used to collect information about any Adverse Events (AEs) or Serious Adverse Events (SAEs) that may have occurred since discharge and to follow-up on any Adverse Events (AEs) that were on-going at discharge.

Assuming an effect size of 0.35 on the change in PANSS total score from baseline to Week 6 for the two pairwise comparisons between each active HP-3070 treatment arm and placebo, the power for detecting a statistically significant HP-3070 advantage will be approximately 0.90 having 204 evaluable subjects per each treatment arm, using a two-sided alpha level of 0.025 for each comparison. A two-sided overall type I error is equal to 0.05. Having three treatment arms, the total number of subjects randomized in the trial and included in primary analysis set will be approximately 612.

The effect size of 0.35 (difference between means equal to 7 and common standard deviation (SD) equal to 20) was chosen based on the lowest effect size observed in results from the studies conducted with sublingual (SL) asenapine and approved by the Food and Drug Administration (FDA) (Sycrest®/SAPHRIS® [Study 041004, and Study 041023]).

A sample size recalculation (SSR) will be conducted as described in Section 4.2 on the blinded data after approximately 50% of the originally planned number of subjects have been randomized and completed up to 6 weeks of study treatment.

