# Table 14.2.1.1.1 Treatment Comparison of Change from Baseline in PANSS Total Score at Week 6Full Analysis Set

		Treatment Group	Treatment Group		
	HP-3070 18.0 mg	HP-3070 9.0 mg	Placebo	HP-3070 18.0 mg	HP-3070 9.0 mg
Statistic	(N=XXX)	(N=XXX)	(N=xxx)	(N=XXX)	(N=XXX)
Baseline					
n	XX	XX	XX		
Mean	х.х	х.х	х.х		
SD	x.xx	x.xx	x.xx		
Median	х.х	х.х	x.x		
Min	х	х	х		
Max	x	Х	х		
leek 6					
Observed					
n	XX	XX	XX		
Mean	X.X	x.x	x.x		
SD	x.xx	x.xx	x.xx		
Median	X.X	x.x	x.x		
Min	х	х	х		
Max	х	х	х		

Note: PANSS = Positive and Negative Syndrome Scale, LSM = Least Squares Mean, SE = Standard Error, CI = Confidence Interval, N = number of subjects in the full analysis set by treatment group.

Note: The PANSS total score is the sum of all 30 items. Higher values represent greater severity of illness. If one or more items are missing at a given assessment, the total score is set to missing.

Note: Baseline is defined as the last non-missing measurement taken prior to first dose of double-blind study medication

Note: The mixed linear repeated measures model includes treatment, country, visit, treatment by visit interaction, and baseline value as covariates, and subject as random effect. The correlation of repeated measures within a subject is estimated with an unstructured covariance matrix. The Kenward-Rogers method is used to estimate the denominator degrees of freedom.

Note: Adjusted p-values are calculated according to the truncated Hochberg procedure with a truncation factor  $\gamma$ =0.9. Adjustment for multiple comparisons uses a parallel gatekeeping procedure. Adjusted p-values are presented for the secondary endpoint CGI-S Score change from baseline only if at least one of the primary hypotheses for the primary endpoint PANSS total score change from baseline are rejected.

Noven\HP-3070\XWA17541\Biostatistics\Production\Tables\xxxxx.sas ddmmmyyyy hh:mm

Author: [name]

Version Number: Version Date:

Draft 2 09Jan2017 Page **35** of **144** 

Noven Pharmaceuticals, Inc.

Protocol HP-3070-GL-04

Page 2 of x

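### The primary MMRM gives baseline PANSS one slope for all six visits; a baseline-by-visit term would protect the Week 6 comparison at almost no cost

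*SAP*

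**What the plan says.** The primary model in SAP 15.1.3 takes change in PANSS total score as the repeated outcome. Its terms are country, treatment, "visit (Weeks 1, 2, 3, 4, 5, and 6"), "treatment by visit interaction, and the Baseline PANSS total score as covariates". The PROC MIXED call agrees: the MODEL and REPEATED statements run "VISIT BASE / ddfm=kr; repeated VISIT / type=un subject=SUBJID", so `BASE` enters once and `BASE*VISIT` does not appear. The shell for Table 14.2.1.1.1 carries the same model in its footnote: "The mixed linear repeated measures model includes treatment, country, visit, treatment by visit interaction, and baseline value as covariates".

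Treatment effects and the covariance matrix are allowed to differ by visit. Baseline and country each enter as a single main effect. Only the Week 6 contrasts of each dose with placebo carry the primary test. Missing PANSS scores are not imputed in the primary analysis. Sections 7.3 and 15.1.3 rely on missingness at random given the observed history and the covariates.

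Sections 15.2.3 (CGI-S), 15.3.1.4 (CGI-I) and 15.3.3.1 (other continuous endpoints) reuse this model with their own baseline covariate. Appendix 3 refits the primary model to each imputed dataset.

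**The concern.** A single slope is an assumption that the relation of baseline severity to change is the same at Week 1 and at Week 6. The SAP neither justifies nor checks it. If it is false, the fitted slope is a compromise across visits, and the adjustment at Week 6, the only visit that matters for the primary test, is wrong.

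Two things follow. First, baseline variation that should have been removed stays in the Week 6 residual, which costs precision. Second, the likelihood predicts the unobserved Week 6 scores of dropouts from their history and baseline. A wrong Week 6 baseline relation mispredicts them whenever dropouts differ from completers in baseline. If that misprediction differs between arms, it does not cancel in the active-placebo contrast.

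Nothing planned would show this. The AIC comparison in 15.1.3 concerns variance heterogeneity between arms, and the residual and influence plots do not look at baseline by visit.

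**Working it through.** **1. The plan's own figure.** Section 3.1 gives a "difference between means equal to 7 and common standard deviation (SD) equal to 20", power of "approximately 0.90 having 204 evaluable subjects per each treatment arm", and a test "using a two-sided alpha level of 0.025 for each comparison". The standard error is 20 × √(2/204) = 1.980. Power by the normal approximation is Φ(7/1.980 − 2.241) = Φ(1.294) = 0.902. The noncentral t gives 0.8986 at 203 and 0.9002 at 204 per arm, so 204 reproduces. This point does not touch the sample size.

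**2. Where the common slope lands.** With complete data and visit covariance Σ, the GLS slope is Σⱼ wⱼβⱼ with w = Σ⁻¹1 / (1′Σ⁻¹1). Assumed inputs: AR(1) correlation 0.7 to 0.9, true slope moving linearly from −0.1 at Week 1 to −0.3 at Week 6.
- Visit SD rising from 11 or 15 to 20: Week 1 gets 46% or more of the weight and Week 6 gets 2% to 20%. The fitted slope is about −0.09 to −0.17.
- Constant visit SD: Weeks 1 and 6 weigh equally and the fitted slope is −0.20, still short of −0.3.

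**3. Precision without dropout.** Let s be the baseline SD, β₆ the Week 6 slope and β_c the fitted common slope. With a Week 6 SD of 20, the residual variance is 400 − (β₆s)² when the slope is right. The common slope adds ((β₆ − β_c)s)².
- Milder change, s = 8, β₆ = −0.30, β_c about −0.107: 400 − 5.76 = 394.2, plus (0.193 × 8)² = 2.4. The SE ratio is √(396.6/394.2) = 1.003.
- Steep change, s = 12, β₆ = −0.60, β_c = −0.142: 400 − 51.8 = 348.2, plus (0.458 × 12)² = 30.2. The SE ratio is √(378.4/348.2) = 1.042.

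Simulation gave SEs of 1.966 against 1.960 (0.3%) and 1.921 against 1.842 (4.3%). By the power formula above, 0.906 becomes 0.908 and 0.920 becomes 0.940 when the term is added, about 0.2 to 2 points of power.

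**4. Shift of the Week 6 difference under MAR dropout.** Simulation with 3 × 204 subjects, true effect −7, Week 6 SD 20 and 1000 replicates per setting. Each dataset was fitted with and without `BASE*VISIT` (ML, unstructured covariance, country left out). Assumed: baseline SD 8 to 12, visit SDs 11 to 20, AR(1) correlation 0.85, arm dropout 21% to 51% where there is any. Entries are the SAP model minus the model with `BASE*VISIT`, in PANSS points, with ranges over baseline SD 8 to 12. Negative values mean a larger apparent drug effect.

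| Dropout pattern | Slopes −0.10 to −0.30 | Slopes −0.10 to −0.60 |
|---|---|---|
| Depends on baseline, more in placebo (49% vs 25%) | −0.24 to −0.36 | −0.61 to −0.90 |
| Depends on baseline in placebo only (39% vs 21%) | −0.36 to −0.53 | −0.89 to −1.31 |
| Opposite dependence by arm (34% each; extreme) | −0.61 to −0.92 | −1.52 to −2.28 |

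Across both slope sets:
- No dropout, or dropout unrelated to baseline: 0.00 to +0.03.
- Same baseline dependence in all arms, 34% each: 0.00 to 0.01.
- Dropout driven by current PANSS level, same rule in all arms (51% vs 45%): −0.03 to −0.18.
- Slopes truly equal: 0.00, even with opposite dependence by arm.

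With `BASE*VISIT` the estimate was unbiased within Monte Carlo error (about 0.07, with the error shared by both fits) in every setting.

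**5. A second set of assumptions.** About 27% dropout, baseline SD 10, slopes from −0.1 to −0.2, −0.3 or −0.5, and dropout hazard changing by a factor of 1.35 per baseline SD. With dependence in one arm only, the effect was understated by 0.07, 0.13 and 0.29 points. With opposite dependence by arm, it was understated by 0.13, 0.25 and 0.52. The sign is the reverse of step 4, so direction depends on the dropout pattern.

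**The case against.** The strongest reply is that the SAP is clear and consistent here: text, code and shells agree, and a main-effect covariate is a legitimate choice. Country is treated the same way, so baseline is not an odd omission. The slopes, baseline SD, early-visit SDs and dropout rates are all assumed. In the mild cases the shift is small beside a Week 6 standard error of about 2. The placebo-based imputation in Appendix 3 uses baseline and prior visits for each visit imputed, and the rank ANCOVA in Appendix 4 regresses on baseline at Week 6. Conclusions therefore do not rest wholly on the common slope.

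Most of this stands, and it sets the weight of the point. It does not remove it. Those two sensitivity analyses also change the missing-data assumption, so neither isolates the slope, and the primary and key secondary tests still use the common one.

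Three stronger readings are tempting and are not supported:
- **That baseline-dependent dropout alone biases the result.** It does not. When dropout behaves alike in all arms, the errors cancel in the contrast.
- **That the drug effect is known to be understated, or exaggerated.** The two sets of simulations point in opposite directions, and the SAP has no figures that would settle it.
- **That the slope is known to change.** The SAP has no data on this; it is a possibility worth guarding against.

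**Conclusion.** The point holds as a minor improvement. The single slope is a fact of the plan; its harm is conditional.

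- **Precision:** if the slope changes over visits, the loss is about 0.3% to 4.3% of the Week 6 standard error without dropout.
- **Bias:** if, in addition, baseline-related dropout differs between arms in dependence or rate, which MAR allows, the Week 6 difference can move either way. The size is about 0.1 to 0.5 points with milder slope change (0.1/7 to 0.5/7, or 1% to 7% of the design effect). It reaches about 1.3 points with steep change (1.3/7, or 19%). Larger shifts appeared only under opposite dependence by arm, an extreme case.
- **Neither condition met:** essentially no shift.

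These sizes rest on the assumed slopes, SDs, correlation and dropout rates. The sponsor cannot know before unblinding whether the conditions hold, and adding the term leaves the expected estimate unchanged if slopes are constant. That asymmetry is the reason to add it.

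**What to change.** Before unblinding, change the MODEL statement in 15.1.3 to `model CHG = TRT COUNTRY VISIT TRT*VISIT BASE BASE*VISIT / ddfm=kr;` and amend the sentence listing the covariates to match. Use the same form where the model is copied: CGI-S in 15.2.3, CGI-I in 15.3.1.4 (with baseline CGI-S) and the other continuous endpoints in 15.3.3.1. Update the shell footnotes that describe the model.

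Using it in the Appendix 3 analysis model is for consistency and precision only. Those datasets are complete after imputation, so the common slope causes no bias there.

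Section 3.3 states that nothing departs from the protocol. If the protocol specifies the main-effect model, record the change there.

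The cost is five parameters in about 612 subjects, plus minor edits to the SAP and shells. No new data are needed and the sample size does not change.
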